## **8. DATA HANDLING AND RECORD KEEPING**

### **8.1. Case Report Forms (CRFs)**

Completed original CRFs are the sole property of Acera and should not be made available in any form to third parties, except for authorized representatives of appropriate regulatory authorities, without written permission from Acera.

It is the Principal Investigator's responsibility to ensure completion of CRFs by the clinical research team and to review and approve the data captured on all CRFs as accurate. All CRFs must be signed by the investigator. This signature serves to attest that the information contained on the CRFs is true. At all times, the investigator has final personal responsibility for the accuracy and authenticity of all data entered on CRFs. Subject source documents are the investigator's subject records maintained at the study site, and will be used to verify data documented on CRFs.

In some cases, a portion of the source documents for a given study/site may be the CRFs. For this study, the patient questionnaires' CRF pages will be considered source documents.

#### **Maintenance of Records:**

The Principal Investigator shall maintain the required records for a period of 2 years after the date the study is completed or terminated or the records are no longer required to support a submission to a regulatory agency, whichever date is later. The Principal Investigator may withdraw from the responsibility to maintain records for the time required by transferring custody to another person who will accept responsibility for them. The sponsor must be notified in writing about the records transfer.

## **9. ETHICS**

### **9.1. Ethical Conduct of the Clinical Study**

This clinical study will be conducted in accordance with the ethical principles that have their origin in the Declaration of Helsinki and in compliance with the protocol, Good Clinical Practice (GCP) guidelines, and applicable local regulatory requirements and laws.

## **9.2. Institutional Review Board (IRB)**

It is the responsibility of the investigator to obtain prospective approval of the conduct of the clinical study, the final protocol, protocol amendments, informed consent forms, and other relevant documents (e.g. advertisements), if applicable, from the IRB. Copies of the final IRB approvals must be forwarded to Acera Surgical, Inc. prior to enrolling patients or starting any clinical study activities.

Protocol amendments require Acera Surgical, Inc. and IRB approval before any patient in this clinical study is subjected to that change. When a change is necessary to eliminate apparent immediate hazards to the clinical study patients, emergency procedures can be used with caution to prevent exposing the patient to the hazard.

## **9.3. Confidentiality**

Information about study patients will be kept confidential and managed according to the requirements of the local regulatory authority, as well as applicable US laws and regulations. Personal Health Information (PHI) will be acquired during informed consent of the patient and from the medical records. This information will be utilized to identify the subject and contact the subject for emergencies and follow up appointments. The PHI is part of the patient clinic chart, and will be secured in a locked office when not in use. To ensure that confidentiality is maintained, patient names will not be used in this evaluation in any other way. A unique identifying number will be used. This identification method will be consistent for each subject throughout the evaluation.

In the event that a patient revokes authorization to collect or use PHI, the Investigator, by regulation, retains the ability to use all information collected prior to the revocation of the authorization.

## **10. SPONSOR DISCONTINUATION CRITERIA**

The Sponsor may suspend or terminate the study or part of the study at any time for any reason. If the investigator suspends or terminates the study at their respective site, the investigator will promptly inform the Sponsor and the IRB/EC and provide them with a detailed written explanation.

### **10.1. Termination of the study by the Sponsor**

Premature termination of this clinical study may occur because of a regulatory authority decision, change in opinion of the IRB/EC, product safety concerns or at the discretion of Acera Surgical, Inc.

Acera Surgical, Inc., reserves the right to discontinue the study prior to inclusion of the intended number of patients, but intends only to exercise this right for valid scientific or administrative reasons. After such a decision, the investigator must contact all participating patients within 30 days.

### **10.2. Termination of Site by the Sponsor**

Acera Surgical, Inc., reserves the option to terminate the participation of a study site at any time. Reasons for terminating the participation of a study site include, but are not limited to, the following:

- Patient enrollment is unsatisfactory
- Data recording is consistently inaccurate or incomplete
- Investigator does not adhere to the protocol or applicable regulatory guidelines in conducting the study
- IRB decides to terminate or suspend approval for the Investigator
- Study site or Investigator violates GCP or the study agreements, disrupting the appropriate conduct of the trial.
- Investigator asks to withdraw from study participation

### **10.3. Termination by the Investigator**

If the Investigator terminates the study prematurely, the Investigator must provide the Sponsor and IRB/EC with a written statement describing why the study was terminated prematurely.

## **11. PUBLICATIONS POLICY**

Acera Surgical, Inc. will be responsible for determining when the study results should be published. The Sponsor may work jointly with the investigators to publish information. The investigators shall not submit a publication to journals or professional societies without notification and review by the Sponsor.

## 12. SUMMARY OF PROTOCOL REVISIONS

Revision Number	Date	Sections Revised	Summary of Changes
01	xx/xx/21		
02	21OCT2022	4.1 inclusion #7; 4.1 inclusion #8b; 4.2 exclusion #16 5.4 5.4.1 5.4.2 5.5 5.6 5.12 7.6.1 Appendix B	Including wounds $\leq 30\text{cm}^2$ , remove lower limit on wound size, remove upper ABI limit, run-in period revised to remove wound size changes limitations, remove acetate tracing requirements, data analysis will be conducted using chi squared

## 14. APPENDICES

### Appendix A: Schedule of Events

Requirement	Run-In Period		Treatment Period (1)											Two-Week In-person Follow-up (2)	
	Start	7 days (±3 days)	0	1	2	3	4	5	6	7	8	9	10	11	12
															2 weeks after wound closure (±3 days)
Informed Consent	X														
Screening	X	X	X												
Demographic and history	X														
HbA1c	X(3)														
Vascularization (ABI, TBI or TcPO2)	X(3)														
Assessment of Re-Epithelialization				X	X	X	X	X	X	X	X	X	X	X	
SF-36 Questionnaire and Pain Scale			X												X(4)
Randomization			X												
Visual Examination of Wound and imaging	X	X	X	X	X	X	X	X	X	X	X	X	X	X	
Product Application			X	X	X	X	X	X	X	X	X	X	X	X	
Adverse events			X	X	X	X	X	X	X	X	X	X	X	X	X(2)

**Notes:**

- X – Requirement must be completed by study personnel
- (1) – Treatment period visits will cease after complete wound re-epithelialization is confirmed
- (2) – An in-person visit two weeks (± 3 days) after complete wound re-epithelialization is first identified after Week 0 are required for patients with complete wound re-epithelialization. These visits are NOT required if there is not complete wound re-epithelialization at or before 12 weeks.
- (3) – HbA1c and a vascularization assessment can be completed anytime within 60 days prior to Week 0
- (4) – SF-36 Questionnaire and Pain Scale will be completed during the visit when complete wound re-epithelialization is first identified or at 12 weeks (whichever occurs first)

## Appendix B: Randomization Plan

# A Randomization Plan for patients with wound size < 12.5 cm^2

from

<http://www.randomization.com>

1. Standard of Care \_\_\_\_\_
2. Restrata \_\_\_\_\_
3. Restrata \_\_\_\_\_
4. Standard of Care \_\_\_\_\_
5. Restrata \_\_\_\_\_
6. Standard of Care \_\_\_\_\_
7. Restrata \_\_\_\_\_
8. Standard of Care \_\_\_\_\_
9. Restrata \_\_\_\_\_
10. Standard of Care \_\_\_\_\_
11. Restrata \_\_\_\_\_
12. Standard of Care \_\_\_\_\_
13. Standard of Care \_\_\_\_\_
14. Restrata \_\_\_\_\_
15. Restrata \_\_\_\_\_
16. Restrata \_\_\_\_\_
17. Restrata \_\_\_\_\_
18. Standard of Care \_\_\_\_\_
19. Standard of Care \_\_\_\_\_
20. Restrata \_\_\_\_\_
21. Standard of Care \_\_\_\_\_
22. Restrata \_\_\_\_\_
23. Standard of Care \_\_\_\_\_
24. Standard of Care \_\_\_\_\_

24 subjects randomized into 2 blocks

To reproduce this plan, use the seed 24156

along with the number of subjects per block/number of blocks  
and (case-sensitive) treatment labels as entered originally.

Randomization plan created on 3/26/2021, 1:14:54 PM

**A Randomization Plan for patients with wound size  
of  $\geq 12.5 \text{ cm}^2$  and  $\leq 30 \text{ cm}^2$**   
from  

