### **5.6. Randomization**

The randomization process will be finalized prior to enrollment of the first study patient. Once the patient meets all enrollment criteria and has completed the 2-week run-in period, the patient will be randomized. Patients will be randomized to receive either synthetic hybrid-scale fiber matrix (treatment group) or standard of care treatment (control group). Appendix B presents the randomization plan.

Randomization will be stratified by wound size:

Patients will fall into two groups ( $< 12.5 \text{ cm}^2$ ) and ( $\geq 12.5 \text{ cm}^2$  and  $\leq 30 \text{ cm}^2$ ). Patients within each group will be randomized in a 1:1 ratio to receive either synthetic hybrid-scale fiber matrix or standard of care treatment.

Once the patient is ready to be randomized, the randomization form will be completed by study personnel. Any patients that exit the study before randomization

are considered screen failures. A study exit CRF shall be completed if the patient is not eligible for randomization.

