**<http://www.randomization.com>**

1. Standard of Care \_\_\_\_\_
2. Restrata \_\_\_\_\_
3. Standard of Care \_\_\_\_\_
4. Restrata \_\_\_\_\_
5. Standard of Care \_\_\_\_\_
6. Restrata \_\_\_\_\_
7. Restrata \_\_\_\_\_
8. Standard of Care \_\_\_\_\_
9. Restrata \_\_\_\_\_
10. Restrata \_\_\_\_\_
11. Standard of Care \_\_\_\_\_
12. Standard of Care \_\_\_\_\_
13. Standard of Care \_\_\_\_\_
14. Restrata \_\_\_\_\_
15. Restrata \_\_\_\_\_
16. Standard of Care \_\_\_\_\_
17. Restrata \_\_\_\_\_
18. Restrata \_\_\_\_\_
19. Standard of Care \_\_\_\_\_
20. Restrata \_\_\_\_\_
21. Standard of Care \_\_\_\_\_
22. Standard of Care \_\_\_\_\_
23. Standard of Care \_\_\_\_\_
24. Restrata \_\_\_\_\_

24 subjects randomized into 2 blocks  
To reproduce this plan, use the seed 27186  
along with the number of subjects per block/number of blocks  
and (case-sensitive) treatment labels as entered originally.  
Randomization plan created on 3/26/2021, 1:17:57 PM

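### Appendix B prints the full ordered allocation list and seed for both strata, and the protocol describes no way of concealing the next assignment

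*Combined protocol and SAP*

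**What the plan says.** Section 5.6 stratifies by wound size (below 12.5 cm², and 12.5 to 30 cm²) with 1:1 allocation in each stratum. It states: "Appendix B presents the randomization plan". Appendix B then prints 24 numbered assignments for each stratum, names the website that produced them, says that 24 subjects are in 2 blocks, and ends each list with its seed: "To reproduce this plan, use the seed 24156" and "To reproduce this plan, use the seed 27186".

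On how an assignment is made, Section 5.6 says three things:

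- "The randomization process will be finalized prior to enrollment of the first study patient".
- Randomization takes place after eligibility has been confirmed and the run-in is over.
- At that point "the randomization form will be completed by study personnel".

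No section names envelopes, a telephone or web system, a list holder, or a protocol copy without Appendix B. The independent statistician in Section 7.4 works on the interim analysis and has no role in allocation. Section 3 gives two sites and masks the subject only. Section 5.7 covers the patient only, from assignment onward. Section 9.2 puts the protocol in the investigator's hands: "It is the responsibility of the investigator to obtain prospective approval of the conduct of the clinical study, the final protocol".

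**The concern.** Allocation concealment means that whoever decides on entry cannot know the next assignment. It is separate from blinding after assignment, and an open-label trial needs it just as much. Here the sequence sits in a document that the sites work from.

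Two decisions could be influenced:

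- **Eligibility.** Several exclusions in Section 4.2 rest on the investigator's judgment, for example metabolic control, critical colonization and life expectancy. Appendix A repeats screening at Week 0, the randomization visit.
- **Stratum.** A wound measuring close to 12.5 cm² could be placed in whichever list offers the preferred arm. This assumes that the Week 0 area after debridement sets the stratum. Section 4.1 uses that area for the 30 cm² limit, but Section 5.6 does not say which measurement decides the stratum.

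A patient who leaves before randomization is a screen failure (Section 5.6). Under Sections 5.5 and 7.2 the ITT population contains only enrolled, that is randomized, patients. Selection by expected healing would therefore act before the ITT, mITT and PP sets exist, and neither those sets nor the multiple imputation in Section 7.8 could recover it. At 24 per arm, one patient is 1/24, or about 4 percentage points of an arm's closure rate.

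**Working it through.** **1. The lists agree with their own description.** R = Restrata, S = Standard of Care, split into blocks of 24/2 = 12.

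| Stratum | Entries 1–12 | Entries 13–24 | R:S |
|---|---|---|---|
| < 12.5 cm² | SRRSRSRSRSRS (6:6) | SRRRRSSRSRSS (6:6) | 12:12 |
| ≥ 12.5 cm² | SRSRSRRSRRSS (6:6) | SRRSRRSRSSSR (6:6) | 12:12 |

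These are complete, working 1:1 lists, 48 assignments in total.

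**2. What printing the list adds.** Suppose the list were withheld and someone knew only the block size of 12 and all past assignments. An assignment is then certain only once one arm of the block is full. Counting the forced entries block by block gives 1 + 2 + 2 + 1 = 6 of 48. Guessing the arm with more places left, and scoring ties as one half, would be right for 16/24 and 16.5/24, or 32.5 of 48. With the printed list and a known position, 48 of 48 are certain.

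**3. How many assignments one site could foresee.** Section 5.6 does not say whether the two sites share each list or divide it.

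- Lists divided by site, or shared with the other site's count known: all 48.
- Lists shared, other site's count unknown: the position has to be inferred. In the simulation (4,000 accruals per list) each slot belongs to the site with probability *q*. The site knows *q*, updates its belief about its position from its own past assignments, and guesses the likelier arm. A coin toss scores 50%.

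| Site's share *q* (assumed) | Correct guesses, averaged over the two lists |
|---|---|
| 10% | about 53% |
| 30% | about 57% |
| 50% | about 62% |
| 70% | about 73% |
| 90% | about 90% |

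Weighted by enrolment, a 70/30 split gives 0.7 × 73 + 0.3 × 57 ≈ 68%. A 90/10 split gives 0.9 × 90 + 0.1 × 53 ≈ 86%.

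**4. Illustration of what steering could do to the test.** The amount of steering is assumed; the documents give no figure for it. Set the true closure rates at 50% and 40%, exactly at the +10-point margin, where a one-sided 5% test should succeed about 5% of the time. Swap *k* patients in total, half into each arm, whose healing chances differ by *d*. The difference between arms then shifts by *k* × *d*/24, split equally between the arms' binomial rates. Rejection means Farrington-Manning z ≥ 1.645, by exact enumeration of all outcome pairs.

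| Swapped *k* | Gap *d* | Shift (points) | Rates used | Rejection, 24 per arm | Rejection, 20 per arm |
|---|---|---|---|---|---|
| 0 | – | 0 | 50.0 / 40.0% | 5.05% | 4.7% |
| 2 | 30 points | 2.5 | 51.25 / 38.75% | 7.1% | – |
| 2 | 40 points | 3.3 | 51.7 / 38.3% | 7.9% | – |
| 4 | 30 points | 5.0 | 52.5 / 37.5% | 9.8% | 8.7% |
| 4 | 40 points | 6.7 | 53.3 / 36.7% | 11.9% | 10.5% |

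The 20-per-arm column uses the evaluable number in Section 7.3 with the same shifts in points.

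**The case against.** The strongest reply is that printed in this document does not mean visible to the person enrolling. Section 5.6 says the process would be finalized before the first patient, so a separate procedure may exist. Section 9.2 shows that the investigator submits the protocol, not that every enrolling coordinator's copy carried Appendix B. This stands as a limit: actual foresight or misuse is not shown. It does not remove the defect. No procedure or restricted copy is described, and envelopes or central release would not conceal a sequence that the protocol itself prints.

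Second, the plan has partial safeguards. Eligibility and the run-in must be complete before randomization. Ulcer size is assessed at both run-in visits, the wound is imaged there and at Week 0, and Section 5.2 requires a screening log with reasons for exclusion. These would expose gross misclassification and let screen-outs be audited afterwards. They do not stop a borderline judgment made with the next assignment known, because nothing fixes eligibility or stratum before the assignment can be seen.

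Third, the numerical illustration is soft. The size of the steering is assumed, the calculation swaps patients between arms rather than screening them out, and it ignores the sample size re-estimation. The high predictability figures for shared lists apply to the larger site only. All of this is fair. The illustration shows a direction and a plausible scale, and the conclusion does not depend on it.

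**Conclusion.** The concern holds, and the plan must be changed. Two facts can be checked on the page: all 48 assignments are printed in order with both seeds, and no concealment method is described. Followed as written, the plan leaves the sequence readable to staff who are not masked.

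How far this could be exploited depends on things the documents do not state. All 48 assignments are foreseeable if the lists are divided by site or the enrolment counts are known. With shared lists and unknown counts, a single site would guess right about 53% to 90% of the time for assumed shares of 10% to 90%. Moving a borderline wound between strata further assumes that the Week 0 area decides the stratum. Under the assumed steering of two to four patients, false-positive risk at the margin rises from about 5% to between 7% and 12% at 24 per arm. Any bias of this kind would enter before the analysis populations form and could not be corrected afterwards.

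**What to change.** - Remove both lists and both seeds from the protocol.
- Have a statistician independent of the sites generate new lists with an undisclosed seed. The one already engaged for the interim analysis could do this.
- State in Section 5.6 how the two sites draw from each list, and which wound measurement sets the stratum.
- Release assignments one at a time, by central release or sequentially numbered sealed opaque envelopes, and only after eligibility and stratum have been recorded.
- If enrolment has begun, keep the assignments already made, apply the new procedure to the rest, and report that the earlier ones came from a printed list. The screening log can be used to describe screen-outs in that period.

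The cost is small: one amendment with sponsor and IRB approval under Section 9.2, new lists, and a release mechanism for two sites, with no extra patients or visits. Assignments already made from the printed lists cannot be repaired, so delay adds to the loss.

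A separate, minor point while new lists are being made: the printed 24 + 24 places cover 48 patients only if the strata fill exactly evenly. They cover no increase toward the cap of 70 in Section 7.4, so the new lists should be longer.

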**<http://www.randomization.com>**

1. Standard of Care \_\_\_\_\_
2. Restrata \_\_\_\_\_
3. Standard of Care \_\_\_\_\_
4. Restrata \_\_\_\_\_
5. Standard of Care \_\_\_\_\_
6. Restrata \_\_\_\_\_
7. Restrata \_\_\_\_\_
8. Standard of Care \_\_\_\_\_
9. Restrata \_\_\_\_\_
10. Restrata \_\_\_\_\_
11. Standard of Care \_\_\_\_\_
12. Standard of Care \_\_\_\_\_
13. Standard of Care \_\_\_\_\_
14. Restrata \_\_\_\_\_
15. Restrata \_\_\_\_\_
16. Standard of Care \_\_\_\_\_
17. Restrata \_\_\_\_\_
18. Restrata \_\_\_\_\_
19. Standard of Care \_\_\_\_\_
20. Restrata \_\_\_\_\_
21. Standard of Care \_\_\_\_\_
22. Standard of Care \_\_\_\_\_
23. Standard of Care \_\_\_\_\_
24. Restrata \_\_\_\_\_

24 subjects randomized into 2 blocks  
To reproduce this plan, use the seed 27186  
along with the number of subjects per block/number of blocks  
and (case-sensitive) treatment labels as entered originally.  
Randomization plan created on 3/26/2021, 1:17:57 PM

## **Appendix C: Supplies Provided by Sponsor**

- Clinical Report Forms (CRFs)
- Study binder
- Acetate tracing supplies
